#### A pilot study of remotely-delivered (tDCS) combined with cognitive training in adults with multiple sclerosis (MS) (S15-01189)

fatigue (pre- and post-								
Visual analog scale for pain (pre-, early-, mid- and post-session)		Х	X	X	X	X		
Tolerability questionnaire - administered by study staff (pre- and post-session)			X		X			
Safety and tolerability questionnaire –self-report (pre- and post-session)			X		X			
Score for Computerized cognitive games (daily)*			Х		Х			
Daily assessment of sleep			Х		X			
Patient and Caregiver Questionnaires*						Х		
Participant Evaluation of Study Procedures*			Х	Х	X	Х		
Count of successful tDCS sessions (confirmation code by session days)			X	X	X	X		
Optional measures that may b	e exclude	d based on s	tudy persor	nel judgem	ent are indicat	ed by an aster	risk.	

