# e)Analytic Plan:

Specific Aim 1 is to determine feasibility; to be measured by the number of participants successfully completed using the proposed protocol for training and monitored administration. As would be expected, there is a high rate of compliance for in-clinic tDCS administration and therefore remotely-supervised administration should be designed to be similarly compliant. Study success will be defined by 80% participants having completed 80% sessions, shown to be the target compliance for previous tDCS studies. We will also determine the effectiveness of our sham procedures to ensure blinding, as tested by comparing those who accurately identified the sham condition. We will assess whether the frequency or type of side effects differ between the active and control conditions and whether they occur at the same rate as reported from studies of in-clinic administration. Secondary outcomes will be tolerability, participant-reported adverse events, and comparisons of active and control conditions on these measures.

Specific Aim 2 will be to determine preliminary signals for efficacy, and to have pilot findings to determine necessary sample sizes for an adequately-powered clinical trial. For each participant, change scores will be calculated between baseline and study end scores on measures of fatigue and cognitive functioning. These difference scores will then be described and compared between groups (t-tests and ANOVA related analyses) to determine signals of efficacy for active tDCS paired with cognitive remediation vs. active tDCS paired with non-adaptive puzzle and board games vs. sham tDCS paired with cognitive remediation.

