An adverse event is defined as any rating (at any time) of pain of greater than "moderate" or side effects or sensations that arise preceding, during, or following stimulation. Pain and tolerability are measured before, during and after each session. As noted, there is an extensive body of literature demonstrating the safety and tolerability of tDCS both in MS and in a range of clinical disorders. Our lab at Stony Brook Medicine administered >200 active tDCS sessions to MS participants with no pain ratings of severe or greater and no discontinued session (for any reason, safety or tolerability). Figure 3 below demonstrates these results.

Figure 3. Self-applied tDCS sessions across n=20 participants

We will submit study data safety monitoring reports to the IRB after 10 participants are enrolled in the active condition, and follow with reports for each further increment of 10 active enrollees.

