# **Statistical Analyses**

Analyses will be completed with IBM SPSS v. 23. Means, medians, standard deviations (SD) will be compared between subgroups on the measures using conventional cut-off points for each of the symptoms will be compared.

Specific Aim 1 will be tested by comparing the number of participants in each condition meeting the study definition of compliance (having completed 80% sessions). We will also determine the effectiveness of our sham procedures to ensure blinding, as tested by comparing those who accurately identified the sham condition. We will assess whether the frequency or type of side effects differ between the three conditions and whether they occur at the same rate as reported from studies of inclinic administration.

Specific Aim 2 will be to determine preliminary signals for efficacy, and to have pilot findings to determine necessary sample sizes for an adequately-powered clinical trial. For each participant, change scores will be calculated between baseline and study end scores on measures of fatigue and cognitive functioning. These difference scores will then be described and compared between groups (t-tests and ANOVA related analyses) to determine signals of efficacy.

Cognitive performance will be evaluated for those who completed at least 18 sessions. We conservatively plan for comparison of 15 participants in each group, allowing for up to 33% dropout. While both cognitive remediation groups are expected to improve with cognitive training, we hypothesize that the active tDCS condition will gain one standard deviation (of the published normative mean) or more in score than the sham condition and that the group with active tDCS paired with non-adaptive puzzle and board games will neither improve nor decline.

Secondary outcomes will be used to compare the groups in change in performance on the additional measures listed in Table 2. These are the most commonly-used outcome measures in MS trials

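### Adverse events compared between arms can include symptoms present before stimulation, because no rule limits the count to new or worsened symptoms

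*Combined protocol and SAP*

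**What the plan says.** The only definition of an adverse event is in Section IX, Monitoring. It has two parts. The first is any pain rating above moderate, whenever it is given. The second is "side effects or sensations that arise preceding, during, or following stimulation". The same paragraph adds: "Pain and tolerability are measured before, during and after each session".

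Table 2 gives the timing. The pain scale is completed before the session, early in it, midway and afterwards. The staff-administered and self-reported tolerability questionnaires are completed before and after the session. None of the three carries the asterisk that marks optional measures.

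The outcome is set in Section V(e), Analytic Plan, where the Aim 1 secondary outcomes "will be tolerability, participant-reported adverse events, and comparisons of active and control conditions on these measures". Section IX, Statistical Analyses, adds: "We will assess whether the frequency or type of side effects differ between the three conditions". Neither section mentions the pre-session rating, a requirement that the event be new or worse, or attribution to stimulation. Neither says whether the unit of analysis is the participant or the session.

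**The concern.** A rating made before any current flows can meet the definition, and it says nothing about whether active stimulation is tolerated less well than sham. The population can be expected to bring such symptoms: in its account of fatigue, Section III lists pain, spasms and trigeminal neuralgia among the contributors in MS. Each participant has up to 40 sessions, so there are many occasions for a background symptom to be counted.

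Randomisation makes the background equal across arms in expectation. That prevents a spurious difference but does not prevent dilution. Events unrelated to stimulation that are added equally to every arm make the arms look more alike than they are. This pilot is meant to establish a protocol for later trials, so a tolerability result biased towards no difference would be carried into their design.

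**Working it through.** **No figure to reproduce.** The documents give no expected rate, sample-size basis, alpha or power for the adverse-event comparison. The check is of the direction of bias, with assumed rates to show the range.

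**Step 1: can a pre-stimulation rating enter the outcome?** The Monitoring definition admits it (pain at any time; sensations arising before stimulation). Table 2 collects it (pre-session pain scale and questionnaires). Section V(e) compares participant-reported adverse events between arms, and no other definition of the term exists. No section removes pre-session ratings from the count. So the rule as written lets them in.

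**Step 2: direction.** Let p be the probability of an event caused by stimulation or by the sham procedure, and b the probability of a background event, equal in all arms and independent of p.

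- Counted rate = 1 − (1 − p)(1 − b)
- Counted difference = (1 − b) × (p_active − p_sham)

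Any b above zero shrinks the difference by the factor (1 − b) and moves the ratio towards 1.

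**Step 3: range, with the session as unit.** Assumed true rates are 30% active and 10% sham. For example, at b = 0.10: active 1 − 0.70 × 0.90 = 0.370; sham 1 − 0.90 × 0.90 = 0.190.

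| b (assumed) | Active | Sham | Difference | Ratio |
|---|---|---|---|---|
| 0 | 0.300 | 0.100 | 0.200 | 3.00 |
| 0.05 | 0.335 | 0.145 | 0.190 | 2.31 |
| 0.10 | 0.370 | 0.190 | 0.180 | 1.95 |
| 0.30 | 0.510 | 0.370 | 0.140 | 1.38 |

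**Step 4: range, with the participant as unit (ever or never).** Background accumulates over 40 sessions. With an assumed per-session background probability q and sessions treated as independent, the chance of at least one background event is 1 − (1 − q)^40. This is 18% for q = 0.5%, 33% for 1%, 55% for 2% and 87% for 5%. Real symptoms cluster within people, so independence overstates this for a given q. With assumed true ever-event rates of 60% active and 25% sham:

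| b (assumed) | Active | Sham | Difference | Ratio |
|---|---|---|---|---|
| 0 | 0.600 | 0.250 | 0.350 | 2.40 |
| 0.1 | 0.640 | 0.325 | 0.315 | 1.97 |
| 0.3 | 0.720 | 0.475 | 0.245 | 1.52 |
| 0.5 | 0.800 | 0.625 | 0.175 | 1.28 |
| 0.9 | 0.960 | 0.925 | 0.035 | 1.04 |

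**Step 5: which part of the definition matters.** Pain counts only above moderate, and Section IX reports no pain rated severe or worse in more than 200 earlier active sessions. The sensation part, on its plain reading, has no severity threshold. It is the likelier source of background events.

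**Step 6: which reference rating.** The rating before the first stimulation session cannot contain carry-over from a study session. A pre-session rating at sessions 2 to 40 can. If it alone is the reference, lasting irritation or headache from an earlier active session becomes baseline and drops out, which could remove real events mainly from the active arms. Both references are therefore needed.

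**The case against.** The best case for the plan has four parts.

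1. **The definition belongs to safety monitoring.** It stands beside the IRB reporting text, where breadth is prudent. Section IV names the secondary outcome as tolerability and side effects, which have their own questionnaires, and no section says those will be counted by the Monitoring definition. This stands in part. For side-effect frequency and tolerability the link is an inference. For participant-reported adverse events, which Section V(e) lists as a compared outcome, this is the only definition available.
2. **The wording may be narrower than it looks.** Sensations that arise before stimulation could mean onset at headset placement, not a chronic symptom. That is a fair reading, but such an event is still not caused by current, and the pain part has no such limit.
3. **The plan also compares events by type.** A comparison confined to electrode-site effects would be diluted less. True, but the plan does not confine it.
4. **Pain adds little.** The earlier MS work supports this (EDSS up to 8.0, no severe pain ratings), though it was a small open-label sample. This stands.

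A reader might also infer that the comparison with published in-clinic rates is unfair. The documents do not support that: they do not say how those studies counted events, and those counts may include background symptoms too.

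**Conclusion.** The point holds at modest size. The stated rule allows pre-stimulation symptoms into a between-arm secondary outcome, and their effect is to pull the active-versus-sham difference and ratio towards no effect. The direction rests on background being equal across arms and independent of stimulation. It does not describe carry-over, which may differ by arm and is part of the effect of treatment.

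The size cannot be set from the documents, because the rates in both tables are assumptions. A reader might infer a definite loss of power. The plan does not support one: it claims no power for this comparison, gives no event rates, and does not name the unit of analysis or say whether the two active-stimulation arms are pooled. Nor do the documents show that every chronic MS symptom will be counted at all 40 sessions, or that pain and sensations contribute equally.

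**What to change.** Keep the broad definition for recording and safety reporting. Add to the Section V(e) and Section IX analysis text, for the between-arm comparison of adverse events and side effects:

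- **Contrast:** each active-stimulation arm against sham. The present wording that side effects "differ between the active and control conditions" is unclear, because one of the two control arms also receives active stimulation.
- **Main count:** events that are new, or worse than the participant's rating before the first stimulation session.
- **Second count:** events that are new, or worse than that session's own pre-stimulation rating.
- **Listing:** pre-session symptoms at sessions 2 to 40, shown separately by arm so that carry-over stays visible.
- **Ratings used:** post-session ratings for side effects; early-, mid- and post-session ratings for pain. Table 2 lists no during-session questionnaire for side effects.
- **Definitions:** what counts as worse on each scale, and whether the unit is the participant or the session.

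The ratings are already collected, so the cost is analysis wording and one extra tabulation. The downside is fewer counted events in the comparison.

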#### I. PURPOSE OF PROTOCOL

The proposed study will test the tolerability and preliminary efficacy of transcranial direct current stimulation (tDCS) combined with a cognitive training program, remotely-delivered using a telemedicine protocol in n=85 adults with multiple sclerosis (MS) and in n=30 adults with Parkinson's Disease. Overall, the enrollment goal for this study shall be n=115. The objective of this study is to establish a study protocol to use in clinical trials to evaluate the efficacy of tDCS to ameliorate two of the most debilitating symptoms of MS that remain without effective treatment: cognitive impairment and fatigue. We developed the protocol to be used for this study at our former institution, Stony Brook Medicine, and have published the results. As described below, it has been tested in n=20 adults with MS with over 192 active sessions. The tDCS administered in our protocol has been very well-tolerated (all sessions successfully completed, no side effects reported to be more than moderate level).

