*we administered 192 active tDCS* sessions in n=20 MS patients receiving 10 open-label sessions over two weeks (approaching the combined published experience of tDCS in MS fatigue). Participants have ranged in age from 30 to 69 years and included individuals with all subtypes (n=6 relapsing remitting, n=12 secondary progressive, n=2 primary progressive), and a range of disability from mild to severe or wheelchair dependent disability (EDSS scores of 1.0 to 8.0). No adverse effects or side effects of severe intensity have been reported in any session, and no session has been discontinued. As seen in **Figure 1**, the most common adverse event reported was skin tingling, and this did not exceed an intensity of "moderate."

Due to both the novelty of tDCS and the option to participate remotely, we have met great interest in our MS patient community with rapid enrollment, limited only by device and staff availability (53 patients on a waitlist over a three-month period). Compliance has been near-universal and all but one participant (95%) completed at least 8 of the 10 study sessions (this study discontinuation was due to personal family events unrelated to tDCS or the study). Further, the majority of participants have reported benefit from tDCS and requested to continue past the study's 10 sessions.

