Of the eight published trials of tDCS to date, three have directly targeted fatigue. As shown in **Table 1**, all three have used sham-controlled crossover designs, and found significant improvement in fatigue following active treatment in either the full group or subset analyses. Each of the three studies varied in their montage with similar results.

Table 1 . tDCS studies of fatigue in MS to date, including our feasibility study and proposed study							
Author (Year)	Sample n	Design	#Sessions, Treatment Montage				
Ferrucci et al. (2014) 	25	Sham-controlled crossover	5 sessions x 1.5 mA motor cortex x 15 minutes				
Saiote et al. (2014 ) 	13	Sham-controlled crossover	5 sessions x 1.0 mA DLPC x 20 minutes				
Tecchio et al. (2014) 	10	Sham-controlled crossover	5 sessions x 1.5 mA x 15 minutes; sensorimotor cortex				
Protocol feasibility study	17	Open-label (remote protocol)	10 sessions x 1.5 mA DLPFC x 20 minutes				

Two of the three studies included analyses to link to the mechanism of benefit, with unclear results. Saiote et al. included MRI and found a correlation between lesion load in left frontal cortex and reduced fatigue following tDCS treatment. In a follow-up second analyses, Tecchio et al. found tDCS treatment was more effective against MS fatigue when the electrode was focused on the bilateral whole body somatosensory area (but changes in S1 and M1 excitability did not correspond to treatment benefit).

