# IV. SPECIFIC AIMS

Specific Aim 1: To test the feasibility of a randomized, controlled remotely-supervised tDCS clinical trial protocol developed specifically for use in MS. Participants (n=85) will be randomly assigned to receive 40 x 20-minute sessions of either active (up to 2.5 mA) paired with cognitive remediation, to two separate control conditions. The first is an active tDCS condition paired with non-adaptive, traditional puzzle and board games and will act as this study's negative control. The second control will act as the study's positive control and will be sham tDCS paired with cognitive remediation. Each study session, regardless of study arm, will be followed by an additional 10 minute computerized training sessions post-stimulation. Each study arm will complete 40 sessions over eight weeks.

The *primary outcome* for feasibility will be the number of participants completing at least 80% or n=32of the targeted 40 sessions. Secondary outcomes will be comparison of tolerability and participant- reported side effects between the two treatment arms.

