# V. DESCRIPTION OF THE PROTOCOL

# The goal of this pilot study is to establish a structured protocol for safe remotely-supervised delivery of 40 consecutive tDCS sessions (active and control conditions) to be used in a randomized, controlled double-blind clinical studies in participants with MS.

*a)* Study Design: Participants will complete a total of 40 sessions across eight weeks: training at baseline with a study technician and then monitoring (through secure online video) by the study technician for the remaining thirty-nine sessions. We will use the most common montage of bilateral dorsolateral prefrontal cortex (DLFPC) placement, with the anodal electrode placed on the left side. This offers ease of reliable electrode placement and wide therapeutic applications. Dose will be up to the target of 2.5 mA with reduction to 2.0, 1.5, or 1.0 mA based on tolerability testing at baseline. At study end, participants in the sham condition will be offered 10 open label active sessions.

**b)** Study Equipment: For the remotely-supervised sessions, participants will be given the speciallydesigned tDCS device and headset, study laptop computer for secure video monitoring with study technician (must have internet access), a detailed reference manual, and a training video. The Soterix mini-CT is uniquely designed for remotely-supervised delivery and requires a one-time use code provided by the study technician to unlock the device for one stimulation session. The device will not operate without correct headset placement and has a single-button option to abort the session. The device will also automatically abort the session if optimal conditions are not maintained. It reports and records a completion code for each session.

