#### **Risk to Participants**

As described above, tDCS poses low risks to participants and our protocol is well-tolerated. To our knowledge, hundreds of tDCS studies in the US have all been designated Non-Significant-Risk (NSR) the lowest risk level (devices that are not: intended as an implant with potential for serious risk to health, safety, or welfare of subject; purported or represented to be for use in supporting or sustaining human life with a potential for serious risks; for use of substantial importance in diagnosing curing, mitigating, treating disease or otherwise preventing impairment of human health with potential for significant risk; otherwise presents significant risk to the health, safety, or welfare of a subject). For these reasons, the Soterix Mini CT, as used in this study, also qualifies as a NSR device. While tDCS remains an investigational technique (simply because no company has applied to the FDA for approval to market tDCS for any given indication), tDCS is a broadly reproduced and tested techniques that is considered effective in modulating brain excitability in a manner that may support learning and with adverse events (different than sham) limited to tingling, itching, and redness that dispel after stimulation stops. In a prior study of use in a vulnerable population (developmentally disabled children), the FDA issued a NSR for tDCS device (see attached letter). The letter provided as an example of the FDA's designation of tDCS devices as IDE. Because of its prior designation of tDCS devices as IDE, trials do not typically seek further declaration. In the letter provided, [name] specifically sought FDA review of the trial due to the use of tDCS in a vulnerable population (developmentally disabled children). To date, hundreds of trials have been designated as non-significant-risk by IRB review which provide its IDE status. Results of completed trials, including our own work in MS using this protocol, have supported the risk designation provided by IRBs. The Stony Brook Medicine IRB confirmed the NSR and IDE status of tDCS for our study

and others at the institution. We have learned that the NYU IRB has also confirmed tDCS devices (including those manufactured by Soterix) as IDE for current ongoing studies at this institution.

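### The compliance hold rule still defines a completer by 5 of 10 sessions, although each MS arm has 40

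*Combined protocol and SAP*

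**What the plan says.** Section IX, Monitoring, contains a hold rule. After the first 10 participants complete, the study pauses for review if compliance in any arm is significantly below the team's earlier rates. A discrepancy means more than a 50% difference between conditions in mean visits completed, or a 50% difference in the number of completers, or both. A completer has done at least half of the sessions, and the figure given for that half is 5 of 10.

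The MS course is longer. Section IV, Specific Aim 1, says "Each study arm will complete 40 sessions over eight weeks", and section V gives the goal as to "establish a structured protocol for safe remotely-supervised delivery of 40 consecutive tDCS sessions". Only the Parkinson's cohort in section XI has 10 sessions, and its monitoring follows section IX.

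The same section schedules safety reports: "We will submit study data safety monitoring reports to the IRB after 10 participants are enrolled in the active condition", and then to "follow with reports for each further increment of 10 active enrollees". The active condition is not defined there.

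**The concern.** The figure 5 of 10 fits a 10-session design. The team's earlier feasibility work had that design (section II: "sessions in n=20 MS patients receiving 10 open-label sessions over two weeks"). Other MS text also looks carried over from a shorter course: the inclusion criteria in section VII still ask for commitment to a two-week training period.

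At stake is a safeguard. The hold rule is meant to show early whether one arm is failing to stay in treatment. If a completer is anyone who reaches session 5, an arm could lose many participants in the second to fourth weeks of an eight-week course and show no deficit in completers.

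**Working it through.** **Inputs.** Completer threshold: 50%, written as 5 of 10 (section IX, Monitoring). MS course: 40 sessions over eight weeks (sections IV and V). Parkinson's course: 10 sessions (section XI). Feasibility target: 32 of 40 sessions (section IV). MS sample 85, allocated 1:1:1; Parkinson's sample 30.

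**1. The plan's figure in its own setting.** 5/10 = 50%, so the fraction and the count agree for a 10-session course. The earlier experience has that length: 192/(20 × 10) = 96% of planned sessions delivered, and 19/20 = 95% completed at least 8 of 10.

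**2. The same figure in the MS arms.** 5/40 = 12.5%, whereas 50% of 40 = 20. The count and the fraction now disagree by a factor of 20/5 = 4. Anyone stopping at sessions 5 to 19 is a completer under one reading and not under the other. The trial's own compliance target is 32/40 = 80%.

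**3. How much the mean-visits criterion makes up.** This is an illustration under simple assumptions: a fraction f of one arm stops at session s, everyone else in that arm finishes, and the comparison arm averages 40 visits. The affected arm's mean is then lower by f × (40 − s)/40. The plan does not say which arm is the base for a 50% difference, so both are shown.

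| Base for the difference | Mean criterion fires if f exceeds (s = 5 / 10 / 19) | Completer criterion at 20 of 40 fires at f of | Completer criterion at 5 sessions |
|---|---|---|---|
| Higher arm (fall > 1/2) | 0.57 / 0.67 / 0.95 | 0.50 | never |
| Lower arm (fall > 1/3) | 0.38 / 0.44 / 0.63 | 0.33 | never |

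For example, with the higher arm as base and s = 10, f must exceed 0.5/(30/40) = 0.67. With the lower arm as base, a 50% excess means the mean has fallen by more than 1 − 1/1.5 = 1/3, so f must exceed (1/3)/(30/40) = 0.44.

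Ten participants over three arms is about 3 per arm. Suppose two of three in one arm stop at session 15. Their mean is (15 + 15 + 40)/3 = 23.3, which is 41.7% below 40, so with the higher arm as base the mean criterion stays silent. Completers at 20 of 40 are 1 against 3, a 67% difference, and the hold applies. At 5 sessions they are 3 against 3, and nothing happens. With the lower arm as base, the mean criterion would catch this case (40/23.3 − 1 = 71%).

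**4. The optional point on IRB reports.** One arm: 85/3 ≈ 28, giving 2 full tens. Both MS arms with active current: 2 × 85/3 ≈ 57, giving 5. Those arms plus the Parkinson's cohort: 57 + 30 = 87, giving 8.

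**The case against.** The rule states 50% before it states 5 of 10, and a sensible team would apply the fraction and use 20. That may well happen, but the text supports either reading, and a rule that can pause a study should give one number. It is also fair that the mean-visits criterion is unaffected and catches heavy early loss, that every session is supervised with stop criteria, and that the team reviews each participant weekly. These keep the point minor. They do not make the threshold right.

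A reader might infer two stronger points, and the documents do not support either.

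- **That the protocol passes off a shorter, weaker exposure as experience with this regimen.** Section I says "We developed the protocol to be used for this study at our former institution", and section X, Risk to Participants, says "Results of completed trials, including our own work in MS using this protocol, have supported the risk designation provided by IRBs". But section II gives the earlier course as 10 open-label sessions, and Table 1 lists it as "10 sessions x 1.5 mA DLPFC x 20 minutes". The difference is disclosed. The word protocol can fairly mean the remote-supervision method, which is how section II uses it and what the title of reference 1 describes.
- **That IRB reports tied to enrolment leave participants unprotected, so reports by completed course or session block are required.** The per-session monitoring, stop criteria and weekly review apply whatever the reporting calendar. Late effects are possible but not shown, and the documents give no accrual forecast from which to size a gap. Such reports are a preference.

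**Conclusion.** The completer threshold is wrong as written for the MS arms. At 5 sessions it stands at 12.5% of the course instead of 50%, and the completer criterion cannot see participants who stop between sessions 5 and 19. This weakens one of two criteria in the hold rule. It does not disable the rule or affect any outcome analysis. The importance is minor.

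The conclusion assumes that the printed count is applied rather than the fraction. The table also rests on the stated pattern of stopping and a comparison arm that averages all 40 visits; it shows direction and is not a forecast. The undefined active condition is a missing definition, worth a phrase but not a fault that changes a result.

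**What to change.** In section IX, Monitoring, define a completer as *a participant who completes at least 50% of scheduled sessions (20 of 40 in the MS arms; 5 of 10 in the Parkinson's cohort)*. State in the amendment that this corrects the hold rule, since it raises the MS threshold from 5 to 20. The cost is one line of amendment text. The downside is that a hold may be triggered slightly more readily.

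Optionally, say in the same section that the active condition counts everyone receiving active current: both MS arms with active tDCS, with the Parkinson's participants either added to the count or reported separately. They should not drop out of the definition, because their monitoring follows section IX. No change to dose, sample size, the description of earlier work or the report calendar is needed.
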